- Vomiting
- Hyperventilation

Adverse events associated with MRI include:

- Malfunctioning of heart pacemakers, defibrillation devices and cochlear implants
- Reaction to contrast media.

IX. STUDY OBJECTIVES

A. Primary Objective

The primary objective of the study is to determine the incidence of adverse local tissue reactions (ALTR) in each THA implanted with the WMT MoM THA System overall and for yearly cross-section intervals from 4-year to 8-year post implant.

B. Secondary Objective

The secondary objectives include:

- To determine whole blood and serum cobalt and chromium metal ion levels for subjects implanted with the WMT MoM THA System overall and for each defined cross-section interval
- To estimate baseline whole blood and serum and serum cobalt and chromium metal ion levels for subjects not implanted with any metal implants, and compare the cobalt and chromium metal ion levels between the implanted subjects and controls (Group-1 vs. Group-2 subjects).
- To compare functional outcomes, as assessed by HOOS score (Hip disability and Osteoarthritis Outcome Score), of subjects implanted with the WMT MoM THA System overall and for each defined cross-section interval in subjects with and without ALTR (Group-1 subjects).
- To compare cobalt and chromium metal ion levels in subjects with and without confirmed ALTR (Group-1 subjects).

X. STUDY DESIGN

A. Study Design

This is a cross-sectional, multi-center study to evaluate outcomes in subjects previously implanted for between 4 and 8 years prior to the study start date. A target of 5 sites, with up to 7 sites total, will participate in this study. Subjects will be identified from Investigator records. Collected data will be evaluated in aggregate and cross-sectioned by year of implantation according to the time that has elapsed between implantation.

B. Sample Size and Subject Cross-Sectioning

There will be two groups of subjects in this clinical study: **Group 1** will consist of subjects previously implanted with the WMT MoM THA System; **Group 2** (i.e., Control Group) will consist of control subjects not implanted with any other metallic devices (excluding dental implants).

The sample size for **Group 1** is 155 THAs that must have been implanted between 4 and 8 years prior to enrolling in this study. This sample size will allow for 35 THAs to be included at each 1-year interval between Years 5 and 8 and 15 THAs to be included in the Year 4 interval (Table 4).

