For each cross-section year, a sample size of 35 hips will give us a two-sided 95% confidence interval for the incidence rate of ALTR with a width no greater than 0.346. With the entire Group-1 cohort (n=155), the width of such a confidence interval will be no wider than 0.163.

The sample size for **Group 2** is 100 control subjects.

Subjects will be identified from Investigator records. Collected data will be evaluated in aggregate and cross-sectioned by year of implantation. Subjects will be cross-sectioned

by the time that has elapsed between implantation and the initial visit (e.g. 4 years, 5 years) using contiguous visit windows (number of years + 6 months).

As subject enrollment will be carried out in at least 5 sites, enrollment will begin with Group-1. Group-2 subjects will be matched by age and gender to Group-1 to achieve a more balanced distribution between the two groups. To minimize the potential of overenrollment, the study team will generate enrollment summaries and inform the sites if enrollment targets are reached for any given cross-sectioned year or for Group-2.

Table 4. Group 1 enrollment stratification based on time lapse from MoM THA implantation date to initial study visit.

Group 1	Year 4 + 6m	Year 5 + 6m	Year 6 + 6m	Year 7 + 6m	Year 8 + 6m
N (hips)	15	35	35	35	35

In comparing metal-ion levels between Group-1 and Group-2, we will have 90% power to detect a 0.65 standard-deviation unit difference as significant with 5% Type-1 error rate in each cross-sectioned year assuming that the ion levels in Group-1 and Group-2 will have similar variability. With the comparison of the entire Group-1 with Group-2, we can detect 0.4 standard-deviation unit difference as significant with 90% power and 5% Type-1 error rate.

Due to potentially enrolling both hips of a given patient, whenever data is collected for the patient, not for each hip, the data analysis for that particular study objective will be carried out at the patient level. If the data is collected for each hip for a given study objective, the data analysis will be carried out for each hip assuming that the hips are independent.

C. Primary Endpoint

The primary endpoint is an estimate of the incidence of ALTR in each THA implanted with the WMT MoM THA System overall and for each yearly defined cross-section interval.

D. Secondary Endpoints

The secondary endpoints include:

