Group 1: Investigators will attempt to identify potential subjects from those they have previously implanted at their individual practices. Investigators will review their records for consecutive subjects starting with those implanted closest to 8 years from the protocol approval date with the study components and moving forward in time. The Investigator should not skip any potential subject implanted with the appropriate combination of components. Potential subjects will be cross-sectioned using the methods described above. The Investigator should attempt to contact any previously implanted subject that satisfies the Inclusion/Exclusion Criteria until there is a total of 35 subjects enrolled collectively at all sites for each year window (+ 6 months).

Please note: previously implanted subjects with a pending revision of the WMT MoM components are eligible for enrollment and will need to be screened.

If a subject has appropriate WMT MoM components implanted in both hips, both can be enrolled in the study, as long as both hips satisfy the Inclusion/Exclusion Criteria. Subjects will be asked to sign two consent forms and complete two sets of questionnaires, one for each hip, but have only one blood draw and one MRI, if sufficient. Each THA will be assigned to the appropriate cross-sectioning interval (e.g. the two THAs may be in different intervals if bilateral THAs were not performed simultaneously).

Group 2 (Control Subjects): Investigators will attempt to identify potential control subjects from their individual practices as long as the subjects satisfy the Inclusion/Exclusion Criteria. Each subject can only be enrolled one time (see above for Group-2 enrollment guidelines).

Group 1 & 2: The Investigator will inform potential subjects of all aspects of the study, including all potential risks and benefits. Potential subjects will be allowed ample time to consider and ask questions about the information they have been provided. If after being informed the potential subject still wishes to participate, they will be asked to sign an Informed Consent document. Once the subject has signed the Informed Consent document and has met the Inclusion/Exclusion Criteria, they will be considered enrolled in the study. Any subject who signs the Informed Consent document and fails to satisfy the Inclusion/Exclusion Criteria will be considered a screen failure. Screen failures will be captured in the electronic data capture (EDC) system.

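### Treating a patient's two hips as independent makes the ALTR intervals anti-conservative if correlated pairs are enrolled, and the stated maximum widths hold only under independence

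*Protocol*

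**What the plan says.** Section X.C sets the unit of the primary endpoint: "The primary endpoint is an estimate of the incidence of ALTR in each THA implanted with the WMT MoM THA System". Section X.B counts the sample in hips ("The sample size for Group 1 is 155 THAs") and states the precision in hips. Each year with 35 hips is to give "a two-sided 95% confidence interval for the incidence rate of ALTR with a width no greater than 0.346", and for the whole cohort "the width of such a confidence interval will be no wider than 0.163".

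The same section foresees that both hips of a patient may be enrolled and splits the analysis accordingly. Data collected per patient are analysed per patient. For data collected per hip, "the data analysis will be carried out for each hip assuming that the hips are independent".

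Section XIII.A permits the pairs: "If a subject has appropriate WMT MoM components implanted in both hips, both can be enrolled in the study". It adds that the two hips may belong to different year intervals if they were not implanted at the same time. Section XII.A requires a second consent and respect for the overall enrolment count, but sets no separate limit on pairs. Section XIII.F has each side of the MRI read on its own, and section XIII.E collects a HOOS for each THA, so both are hip-level data. Section XI promises 95% confidence intervals for the primary and secondary endpoints without naming a method.

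**The concern.** Two hips in one patient share the host, including any metal sensitivity, which section XIV.G lists as a route to pseudotumor and ALVAL. They share circulating ion levels and, under section XII.A, the specified component combination. Positive correlation of ALTR within a patient is therefore plausible, and nothing in the protocol argues for independence. The rule is written down, so a SAP that follows the protocol would inherit it. The classification into one-hip and two-hip patients in section X.D applies only to metal ions and does not offset it.

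At stake is the interval around the main result of an FDA-ordered surveillance study. Ignoring positive correlation understates uncertainty about a rate of device harm. The comparison of HOOS by ALTR status is also exposed. Its standard error is too small where both hips of a pair share ALTR status and too large where they differ, so its error has no known direction.

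**Working it through.** **Inputs from the protocol.** 155 hips overall; 35 hips in each of Years 5 to 8 (Table 4); two-sided 95% intervals; stated maximum widths 0.163 and 0.346 (section X.B).

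**Inputs assumed, because the protocol gives none.** f is the share of hips that come from patients with both hips enrolled. rho is the within-patient correlation of ALTR. If b is the share of patients who are bilateral, f = 2b/(1 + b), so b = 0.20 gives f = 0.33 and b = 0.30 gives f = 0.46.

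**Step 1: reproduce the stated widths.** The maximum over all event counts of the exact (Clopper-Pearson) 95% interval width is:
- n = 155: 0.1625, stated as 0.163
- n = 35: 0.3463, stated as 0.346

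The alternatives do not match both figures. For n = 155 and n = 35, Wald gives 0.157 and 0.331, Wald with continuity correction 0.164 and 0.360, Wilson 0.156 and 0.314, and Wilson with continuity correction 0.162 and 0.340. The stated precision is therefore the exact binomial width with every hip counted as an independent observation.

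**Step 2: allow for pairs.** With n hips, nf/2 pairs and incidence p, the variance of the event count is np(1−p) + 2 × (nf/2) × rho × p(1−p) = np(1−p)(1 + f × rho). Hence design effect DE = 1 + f × rho and effective sample size 155/DE. The third column of results is the exact width at that size with p = 0.5. Coverage is that of the planned interval, which ignores pairing, simulated at incidences of 0.1 to 0.3.

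| f, rho (assumed) | DE | 155/DE | Worst-case width | Coverage of planned interval |
|---|---|---|---|---|
| no pairs | 1.000 | 155.0 | 0.163 | about 95.6% |
| 0.10, 0.3 | 1.030 | 150.5 | 0.165 | about 95.2% |
| 0.20, 0.5 | 1.100 | 140.9 | 0.171 | about 94.5% |
| 0.33, 0.8 | 1.264 | 122.6 | 0.183 | about 92.6% |
| 0.46, 0.8 | 1.368 | 113.3 | 0.191 | about 91.4% |

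The worst-case width passes 0.163 once f × rho exceeds about 0.006 (about 0.011 allowing for rounding). Coverage at these incidences falls below 95% only once f × rho exceeds about 0.05, because the exact interval has some slack.

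**Step 3: dependence on incidence.** The figure 0.163 is reached near p = 0.5. With DE = 1.15 (for example f = 0.30, rho = 0.5), the correct overall width is 0.110 at p = 0.1, 0.142 at p = 0.2, 0.160 at p = 0.3 and 0.175 at p = 0.5. At p = 0.2 it is still 0.1624 with DE = 1.5.

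**Step 4: yearly intervals.** The same formula applies within a year, but f then counts only hips whose partner is in the same year. If f × rho = 0.10 in a year with 35 hips, the effective size is 35/1.10 = 31.8 and the worst-case width is 0.363 instead of 0.346. If every pair is split across years, DE = 1 and 0.346 stands.

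**The case against.** The strongest reply is that the problem is only potential. The protocol allows both hips but does not predict how many pairs there will be, and each pair needs a second consent. With few or weakly correlated pairs, the exact interval still covers at least 95%. The protocol does not even commit to the exact method, which is inferred from the widths. Some arguments for correlation are also weak: surgeon and site are shared by unilateral patients too, a single MRI is optional, and the sides are read separately. No hypothesis test or decision threshold hangs on the ALTR estimate, and the assumption is stated openly.

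All of that stands, and it limits the size of the point. It does not rescue the rule, because nothing in the protocol ensures that the pairs will be few or uncorrelated.

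A reader might infer that the ALTR intervals are certainly too narrow and that the promised 0.163 will be missed. The documents do not support this. The bilateral share and correlation are unknown, and an interval computed as planned can never print wider than 0.163. What fails under positive correlation is the claim that this width reflects the real uncertainty at the worst-case incidence.

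**Conclusion.** The point holds conditionally and is of moderate weight. Section X.B fixes an independence analysis for hip-level endpoints, including the primary one, in a design that admits pairs without a separate limit. If pairs are enrolled and ALTR is positively correlated, the interval is anti-conservative, chiefly for the overall cohort. Over the assumed range, the loss runs from nothing of practical importance (coverage still about 95.2%) to about four percentage points (95.6% down to 91.4%), with worst-case overall widths of 0.165 to 0.191. The stated widths are correct arithmetic but conditional on independence, and the protocol does not say so. The estimated incidence is unaffected. At an incidence of about 0.2 or less, the correct overall width stays under 0.163 for every design effect tried (up to 1.5), although it is still wider than the interval that would be reported. The HOOS standard error is affected too, but the protocol gives nothing from which to size that.

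**What to change.** Replace the independence sentence in section X.B with a rule that hip-level endpoints are analysed with the patient as the cluster.

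- **ALTR:** a Clopper-Pearson interval at effective sample size n/DE. Estimate DE once, from the overall cohort, as the cluster-robust (ratio-estimator) variance of the incidence divided by its binomial variance, with a floor of 1. This works in yearly strata with few or no events, where a logit-based clustered interval would break down. If the whole cohort has no events, DE cannot be estimated, so a fallback value should be stated in advance.
- **HOOS by ALTR status:** a mixed model or GEE with the patient as the cluster.
- **Precision statement:** say that 0.163 and 0.346 assume independent hips, and give the widths for a stated range of bilateral share and correlation, as in the table above.

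The cost is protocol and SAP wording and a few lines of code, with no extra subjects, visits or data. The identifier in section XIII.A already carries site, enrolment order and side, so hips can be linked if both hips of a patient keep the same enrolment number; this should be confirmed. The intervals become slightly wider and the stated precision slightly less favourable. Using the overall DE within a year is somewhat conservative where pairs are split across years, and DE will be imprecise if pairs are few, although the correction is then usually small.

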The Interim Data Looks will be provided to FDA beginning six months after the final protocol is approved and every six months for the first two years. Interim reporting will be provided annually beginning Year 3 until study completion.

A final study report will be provided to FDA following study completion and final data analysis.

XII. SUBJECT SELECTION

A. Inclusion Criteria

To be included in **Group 1**, subjects must meet all of the following criteria:

- 1. Has been implanted with appropriate components of the WMT MOM THA System for at least four years +/- six months (i.e. 3.5 years since implantation), but not longer than eight years and six months (i.e. 8.5 years since implantation)
- 2. Has previously undergone primary THA for any of the following:
 - a. non-inflammatory degenerative joint disease including osteoarthritis, traumatic arthritis, or avascular necrosis:
 - b. inflammatory degenerative joint disease including rheumatoid arthritis;
 - c. correction of functional deformity.
- 3. Is willing and able to complete required study visit(s) and assessments
- 4. Plans to be available for the required study visit
- Is capable of providing sufficient blood for sampling according to blood draw procedures
- 6. Is willing to sign the approved Informed Consent document

Previously implanted bilateral subjects can have both THAs enrolled in the study provided: 1) the specified combination of components were implanted in both, 2) all other aspects of the Inclusion/Exclusion Criteria are satisfied, 3) enrollment does not

exceed the subject count specified in the Clinical Trial Agreement and protocol enrollment strategy, and 4) the subject agrees to a second Informed Consent document and data collection specific to the second THA. Enrollment and treatment of a previously unimplanted hip is not permitted in this study.

To be included in **Group 2**, subjects must meet all of the following criteria:

- 1. Does not have a metal implant (total hip, total knee, spinal, etc.) with the exception of dental implants
- 2. Is not an employee of the Investigator
- 3. Is willing and able to provide Informed Consent document
- 4. Is willing and able to attend the requested study visit
- Is capable of providing sufficient blood for sampling according to blood draw procedures

B. Exclusion Criteria

Subjects will be excluded from either study group if they meet any of the following criteria:

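### The primary endpoint is labelled the incidence of ALTR in implanted hips, but the design measures Visit 1 prevalence among hips that still carry the study components

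*Protocol*

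**What the plan says.** The Synopsis, Sections IV, V and IX.A, and the endpoint in X.C all name the primary quantity as incidence of ALTR per implanted hip, overall and by year from 4 to 8. Section X.C reads: "The primary endpoint is an estimate of the incidence of ALTR in each THA implanted with the WMT MoM THA System overall". Section X.B sizes the study on the confidence-interval width for an ALTR incidence rate, and Section XI lists the same incidence for the interim looks.

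The design in Section X.A is: "This is a cross-sectional, multi-center study to evaluate outcomes in subjects previously implanted for between 4 and 8 years". Inclusion criterion 1 for Group 1 (XII.A) begins: "Has been implanted with appropriate components of the WMT MOM THA System for at least four years +/- six months", with an upper limit of 8.5 years. Sections X.E and XIII.D to F give the Visit 1 assessments: HOOS, metal ions and MARS MRI. Only subjects diagnosed with ALTR at Visit 1 return, at one year.

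On revision, Section XIII.A notes that "previously implanted subjects with a pending revision of the WMT MoM components are eligible for enrollment and will need to be screened". No text deals with a hip whose components were removed before contact. The same section requires a consecutive record review: "The Investigator should not skip any potential subject implanted with the appropriate combination of components". It defines the only recorded ineligible cases: "Any subject who signs the Informed Consent document and fails to satisfy the Inclusion/Exclusion Criteria will be considered a screen failure". Retrieval analysis (XIII.H) is limited to enrolled hips.

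**The concern.** An incidence among implanted hips needs every implanted hip in the denominator and every hip that developed ALTR in the numerator. One look at hips still in place supplies neither. It observes no onset and counts no time at risk, and hips whose components are gone are in neither count.

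The loss is related to the outcome on the protocol's own account. Section V quotes FDA's concern about device failure leading to revision. Section XIV.G lists pseudotumor, ALVAL and wear requiring early revision as anticipated device events. Section X.E follows ALTR cases until they are revised.

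At stake is the headline answer of an FDA-ordered surveillance study. A reader given an incidence among implanted hips would take it as the share of implanted hips that developed ALTR. The analysis stage cannot repair this, because a hip revised before consent leaves no required record.

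**Working it through.** **1. The plan's own figures.** Inputs from X.B: n = 35 per interval (Years 5 to 8), n = 155 overall, two-sided 95%. The maximum width of the exact Clopper-Pearson interval over all possible counts is:

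- n = 35: 0.3463, at 17/35 (stated: 0.346)
- n = 155: 0.1625, at 77/155 (stated: 0.163)

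Both reproduce. The half-widths are at most about 17 points per interval and 8 points overall. They describe sampling error in the hips examined and nothing else.

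**2. Quantity named against quantity measured.**

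| | Named (IX.A, X.C) | Measured (X.E, XII.A, XIII) |
|---|---|---|
| Denominator | hips implanted | hips with components in place that enrol |
| Numerator | hips that developed ALTR | hips with ALTR at Visit 1 |
| Removed before consent | belongs in both | in neither, and not recorded |

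This mismatch holds whatever the revision rate.

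**3. Direction and size.** The document gives no revision rate and no expected ALTR rate, so all values below are assumptions. For one interval, let

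- F = share of all implanted hips that have developed ALTR,
- r = share whose components were removed for ALTR before enrolment,
- rO = share removed for other reasons, taken here as free of ALTR,
- p = prevalence in hips in place.

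If ALTR does not resolve and enrolled hips represent all hips in place, then F = r + (1 - r - rO)p. So p = (F - r)/(1 - r - rO), and p < F exactly when r/(r + rO) > F.

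With F = 20%:

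| r | rO | r/(r + rO) | p reported |
|---|---|---|---|
| 5% | 3% | 62.5% | 15/92 = 16.3% |
| 5% | 10% | 33.3% | 15/85 = 17.6% |
| 2% | 8% | 20.0% | 18/90 = 20.0% |
| 1% | 5% | 16.7% | 19/94 = 20.2% |
| 2% | 15% | 11.8% | 18/83 = 21.7% |

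The error runs from 3.7 points too low, through zero, to 1.7 points too high.

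**4. Special case rO = 0.** The shortfall is F - p = r(1 - p). At p = 20%, r = 2%, 5% and 10% give 1.6, 4 and 8 points. At r = 10% the shortfall is about as large as the maximum overall half-width from step 1.

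**5. Yearly pattern, still with rO = 0.** If r rose from 2% at Year 4 to 10% at Year 8 in steps of 2 points, with p = 20% throughout, F would be 21.6, 23.2, 24.8, 26.4 and 28.0%. Weighted 15/35/35/35/35, the overall F is 39.08/155 = 25.2%. The study would report 20% in every interval.

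**6. A combined figure.** Take F = 20%, r = 5%, rO = 10%, so p = 17.6%.

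- The simple form r + (1 - r)p gives 5 + 0.95 × 17.65 = 21.8%, not 20%, because it applies p to hips removed for other reasons.
- Bounds avoid this. The lower bound r + (1 - r - rO)p is 5 + 0.85 × 17.65 = 20.0%. The upper bound r + rO + (1 - r - rO)p is 30.0%. They correspond to none and all of the other or unknown removals having had ALTR.

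**The case against.** - **No criterion requires an unrevised hip.** A reader might infer that only unrevised hips can enrol, or that a completed revision is ineligible because a pending one is eligible. Neither follows. Section XIV.F defines revision as any change to the component configuration, so a partial revision that kept the metal-on-metal components is not clearly excluded. This stands, and the point is therefore confined to hips whose components were removed.
- **A downward bias is not proven.** Removals for other causes also drop out and can offset or reverse the effect (step 3). This stands.
- **A masked trend is not shown.** The protocol plans estimates with intervals and states no test between years. Precision is low in any case: 7/35 has an exact 95% interval of 8.4% to 36.9%. Within one implant cohort r cannot fall with time, but the five intervals are different cohorts. Step 5 is therefore an illustration only.
- **The design is openly cross-sectional and said to follow FDA's recommendations.** Consecutive review without skipping, and eligibility of pending revisions, reduce the selection. They do not remove it, and they do not make a prevalence an incidence.
- **The record review is not a census.** It starts nearest 8 years, moves forward, and contact stops once each window is full. This stands, so the log can cover only the records reviewed.
- **Earlier serious adverse events are collected (XIV.E).** They run back to implantation, but in context this applies to enrolled subjects, and it does not feed the primary endpoint.

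**Conclusion.** The concern holds as a wrong label on the primary quantity and an uncounted, outcome-related loss of hips. What the design estimates is the point prevalence of ALTR at Visit 1 among hips with the study components in place 3.5 to 8.5 years after implantation. The mislabelling needs no assumption.

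The numerical effect does. The reported rate is too low when ALTR's share of prior removals exceeds the true ALTR proportion. That is the expected direction, but the document cannot confirm it. Under the assumed values the error ranges from 3.7 points low to 1.7 points high at a true 20%. It reaches 8 points low in the special case r = 10%, p = 20%, rO = 0. None of this is reflected in the stated intervals.

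Two stronger readings are not supported: that the rates are shown to be biased low, and that the later years are shown to be the most affected. Both need revision counts by reason, which the protocol does not collect.

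**What to change.** 1. In the Synopsis (II) and Sections IV, V, IX.A, X.B, X.C and XI, rename the quantity *prevalence of ALTR at Visit 1 among THAs with study components still in place*, by interval and overall. State that it is not cumulative incidence among implanted hips.
2. During the consecutive record review in XIII.A, have sites log each reviewed hip whose components were already removed or revised, with date and recorded reason (ALTR, other, unknown). Also log the number of hips reviewed per interval as the denominator. Report counts and percentages by interval beside the prevalence. An enrolled hip with an earlier partial revision is logged but stays in p, so that it is counted once.
3. If a combined figure is given, report the bounds r + (1 - r - rO)p to r + rO + (1 - r - rO)p, with unknown reasons counted in rO. Label them supportive: reasons coded in charts differ from MRI findings, revisions done elsewhere may be missed, and the bounds carry no sampling error for p.

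Cost: a short log for records already being reviewed, one extra table, and a protocol amendment, which under Section XV needs FDA and IRB/EC approval. No extra subjects or visits.
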